IRB	Institutional Review Board
ISO	International Organization for Standardization
LOS	Length Of Stay

Subject: smART Plus Comparative Study Protocol - Beilinson

ml	milliliter
MOP	Manual of Procedures
NCT	National Clinical Trial
NIH	National Institutes of Health
NIH IC	NIH Institute or Center
NG	Naso-Gastric
PEEP	Positive end expiratory pressure
PI	Principal Investigator
PPI	Proton Pump Inhibitors
QA	Quality Assurance
QC	Quality Control
REE	Resting Energy Expenditure
SAE	Serious Adverse Event
SAP	Statistical Analysis Plan
SOA	Schedule of Activities
SOP	Standard Operating Procedure
VAE	Ventilator Associated Event
APACHE	Acute Physiology and Chronic Health Evaluation

Subject: smART Plus Comparative Study Protocol - Beilinson

1. Protocol Synopsis

Study Title:	Nutrition Monitoring and Feeding Optimization with the smART+ System
Purpose:	To demonstrate the ability of the smART+ System to optimize the delivery of nutrition
Study Design:	Comparative, prospective, stratified randomization
Study Endpoints:	
Primary:
 
Optimization of the delivery of nutrition by the smART+ System as compared to standard of care, by automatically calculating and administering enteral feeding better than standard of care (REE or Calorimeter).
 
Secondary:
 
- Safe use of the entire system (AE/SAE directly related to any of the system components)- Decrease in ICU length of stay from admission to ICU until the decision discharge ordered- Reduction of VAE- Decrease in ventilation days- Decrease in workload related to nurse GRV time- Convenience of use of the system and the user interface (by subjective staff questionnaire)- Assessment of urine flow monitoring related to patient condition and usability
No. of Subjects:	In Beilinson site: 100 patients; 50 patients per group Approximately 200 subjects will be enrolled for the complete multi-center comparative study (100 per group)
Population:	ICU mechanically ventilated patients
Investigational Sites:	Israel, United States, Europe
Principal Investigator:	[name]
Study Duration:	Overall study duration is estimated to enroll for approximately 1 year. Enrollment rate of up to 5 simultaneous patients per site (→ 20 parallel in all 4 sites). Total participation duration: Treatment between 2 days and up to 14 days
Inclusion/Exclusion Criteria:	
Inclusion Criteria:
 
- Males and females 18 years or older- Patients that have already been admitted to the ICU (no more than 48 hours before enrollment)- Expected to be ventilated at least 48 hours after enrollment.- Patient requires enteral feeding (by naso/oro-gastric feeding tube)

Subject: smART Plus Comparative Study Protocol - Beilinson

Exclusion Criteria:

- Pregnant women
- Known anatomical anomalies of the nose, oral cavity esophagus or the stomach that may prevent/hinder the ability to insert the feeding tube

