1.3. Device Description

The smART+ is a comprehensive modular patient care system intended for ICU patients. At the heart of the system is the console which stores, compiles and displays data from the different system modules.

Directly connected to the console is the hub, this is a smaller unit that is positioned adjacent to the patient's bed and serves as a mechanical and communications port for the various modules.

The system's modular arrangement allows the flexibility to add modules over time, at this stage the system comprises the following modules:

- a) The feeding pump is an integral part of the systems console. The feeding pump is controlled by the console and programed by the user using the console's touch screen.
- b) To correspond with the feeding pump, a single use feeding set equipped with an appropriate administration cassette, is loaded into the console.
- c) The feeding tube is equipped with sensors that guide the user toward proper placement of the feeding tube without the need of a conformational x-ray. The sensors also detect reflux events and conveys that information to the console. A balloon on the feeding tube's exterior may be inflated at times of reflux in order to hinder the advancement of gastric content in the esophagus and prevent it from reaching the patient's lungs.
- d) To relieve pressure and remove access gastric content, a disposable Gastric Residual Volume (GRV) set is connected to the proximal end of the feeding tube. The GRV tube passes through a pinch on the system's hub and is only opened when necessary.
- e) The Resting Energy Expenditure (REE) feature is comprised of a disposable flow rate meter and a reusable CO2 detector piece that are added between the patient's endotracheal tube and ventilation tubes. The REE has the capacity to continually measure the patient's energy

[figure not shown]
⁸ Metheny. Effectiveness of an Aspiration Risk-Reduction Protocol. *Norma A. Nurs Res* (2010)

Subject: smART Plus Comparative Study Protocol - Beilinson

expenditure and deduce the patient's nutritional requirements, according to the following equation:

$$REE = \left[3.941 \left(\frac{VCO_2}{RQ} \right) + 1.11(VCO_2) \right] 1.44$$

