1.7. Device Procedure

The use of the smART+ System is substantially similar to the use of commercially available feeding tubes. The smART+ System includes the added feature of facilitating correct tube placement and alerting when tube is displaced during ongoing use. The system will automatically stop feeding if displacement is detected. If a reflux episode is detected by the system, a balloon located on the tube will automatically inflate to prevent gastric content from regurgitating to the esophagus. The balloon inflation parameters are as follows:

- Maximum balloon pressure: 30 mmHg
- Maximum inflation duration: 5 minutes
- Minimum duration between balloon inflations: as long as the previous inflation period

In addition to tube placement, the system allows to obtain REE measurements and calculates the optimized nutritional values required by the patient. Furthermore, the system optimizes feeding by compensating for any lost feeding time or discarded nutritional content that was discarded via the GRV.

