1.8.2. Known potential benefits

Subject: smART Plus Comparative Study Protocol - Beilinson

As explained above, the various components of the smART+ System must operate as a cohesive system in order to allow feeding optimization as demonstrated in the flowchart below. With validation of the smART+ features during the study, the clinical benefit of the device will be the lowering of risks associated with tube displacement and malpositioning as well as lowering the risks associated with reflux and aspiration.

In addition, the smART+ System is able to continuously measure the patients REE and minimize the risk of overfeeding. Therefore, by reducing overfeeding it not only achieves feeding optimization, but it also reduces the likelihood of reflux episodes due to overfeeding.

2. Objectives and Endpoints

2.1. Primary Endpoint:

 ART MEDICAL PATIENT SAFETY TECHNOLOGY	Number: CRO-C-2822	Date issued: 01-Mar-2021
	Rev.06	Page 15 of 35

Subject: smART Plus Comparative Study Protocol - Beilinson

Optimization of the delivery of nutrition by the smART+ System as compared to standard of care, by automatically calculating and administering enteral feeding better than standard of care (REE or Calorimeter).

Optimization is defined as the ability of the system to provide adequate nutrition (not overfeed or underfeed) when compared to treatment via standard of care.

Evaluation will be conducted based on an analysis and comparison of the following parameters (obtained through the hospital's electronic records for control group and smART+ records for the treated group):

- Patient caloric target set
- Volume of patient nutritional intake value versus actual patient need – this is calculated by assessing the actual nutrition delivered, discarded nutrition in the GRV bags as well as the unused quantity in discarded feed bottles (if applicable).

As part of optimization evaluation, feeding efficiency calculation ((Net nutrition delivered [ml])/ (VTBD [ml])) should be calculated for the days when the patient received enteral feeding that given under medical order, removed from the patient, or stopped feeding that was not renewed until the end of the study. Feeding efficiency should not be calculated for the days that patient has been discontinued from enteral feeding by a medical order.

2.2. Secondary Endpoints:

- Safety

Safe use of the entire system will be assessed based on the occurrence of device related AE or SAE.

- Decrease in ICU length of stay.

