5.2.2. Connecting the patient to the smART+ System

The patient should be connected up to all applicable modules of the smART+ as soon as possible after being enrolled in the study. Connection and use of the smART+ UrineFlow system will be as needed according to PI decision.

Detailed instructions of how to connect a patient to the system can be found in the smART+ User Manual and the accompanying Quick Guides.

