5.5. Schedule of Activities (SoA)

Subject: smART Plus Comparative Study Protocol - Beilinson

Procedures	Screening/ enrollment	Medical Device Placement	Ongoing use	Termination
Day	1	1(T)	Up to 14	1 up to 14
Informed Consent	T+C			
Eligibility Criteria	T+C			
Physical Exam	T+C			
Pregnancy test (if applicable)	T+C			
Videotaping		T+C	T+C	
Vital Signs		T+C	T+C	T+C
REE or calorimeter/spirometer measurement		T+C	T as needed and according to procedures	
Lab Data			T+C	T*+C*
Medical Device Administration		T	T	
GRV Measurements			T+C as needed and according to procedures	
Urine monitoring			T as needed and according to procedures	
Adverse Events	T+C	T+C	T+C	T+C
Concomitant Medication		T+C	T+C	T+C
Information regarding nutritional supplement administration		T+C	T+C	

T – group A – "Treated"

C – group B – "Control"

* - For T only – obtained retroactively 24 hours prior the feeding tube insertion and during the ongoing study

6. Preparation/Handling/Storage/Accountability

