- The two-sample T-test or Non-parametric Wilcoxon-Mann-Whitney Rank sum test for independent samples (as is appropriate) will be applied for testing the statistical significance of the difference in the estimated nursing time that was expended for GRV activities, and the amounts of GRV removed from the patient between the study groups.
- Convenience of use of the system and the user interface scores (by subjective staff questionnaire) will be summarized in an appropriate table by study group
- The two-sample T-test or Non-parametric Wilcoxon-Mann-Whitney Rank sum test for independent samples (as is appropriate) will be applied for testing the statistical significance of the difference in the assessment of urine flow monitoring related to patient condition and usability between the study groups.
- The two-sample T-test or Non-parametric Wilcoxon-Mann-Whitney Rank sum test for independent samples (as is appropriate) will be applied for testing the statistical significance of the difference in ICU length of stay (measured from admission to ICU until the decision to discharge is ordered) between the study groups.
- Chi-square test or Fisher's Exact test (as is appropriate) will be applied for testing the statistical significance of the difference in percent of subjects experiencing Ventilation associated events between the study groups.

9.2.5 Safety:

Adverse events will be coded using the Medical Dictionary for Regulatory Activities (MedDRA, most updated version) terminology and presented in tables by System Organ Class (SOC) and Preferred Term (PT).

Subject: smART Plus Comparative Study Protocol - Beilinson

AE data will be listed individually and summarized by SOC and by PT within a system organ class for each study group.

Frequency of TEAEs (Treatment-Emergent Adverse Events) and device-related adverse events will be summarized in tables by SOC, PT and study group and by seriousness.

Chi-square test or Fisher's Exact test (as is appropriate) will be applied for testing the statistical significance of the difference in percent of subjects experienced any AE, drug-related AE and SAE between the study groups.

Concomitant medications entered into the database will be coded using the World Health Organization (WHO) Drug Reference List, which employs the Anatomical Therapeutic Chemical classification system.

10. Regulatory, Ethical, and Study Oversight Considerations

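### Device-related events are reported only over the whole of group A, so the tables understate risk and uncertainty for a component used in part of the arm, chiefly UrineFlow

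*Combined protocol and SAP*

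**What the plan says.** **The claim.** The synopsis gives the endpoint as "Safe use of the entire system (AE/SAE directly related to any of the system components"). Section 2.2 repeats it: "Safe use of the entire system will be assessed based on the occurrence of device related AE or SAE".

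**Exposure.** Section 5.2.2 says "The patient should be connected up to all applicable modules of the smART+ as soon as possible after being enrolled in the study", then singles out one module: "Connection and use of the smART+ UrineFlow system will be as needed according to PI decision". The urine monitoring row of the Schedule of Activities (5.5) agrees: "T as needed and according to procedures". The balloon sits on the tube, but section 1.7 makes its action conditional: "If a reflux episode is detected by the system, a balloon located on the tube will automatically inflate". Section 1.3 c) likewise says that it "may be inflated at times of reflux in order to hinder" the rise of gastric content.

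**Attribution and reporting.** Section 7.4.1 collects, for each adverse event, a description, times, severity and the relationship to the study product. The causality grades refer to the study device as a whole, and no component item is listed. For the tables, section 9.2.5 says "Frequency of TEAEs (Treatment-Emergent Adverse Events) and device-related adverse events will be summarized in tables by SOC, PT and study group and by seriousness". Section 9.2.1 gives proportions and their 95% confidence intervals by arm. No safety analysis set, module-exposure summary or component-specific denominator is defined.

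**The concern.** The endpoint reaches down to components, but the planned tables stop at the arm. If UrineFlow is connected in only some of group A, a UrineFlow-related event rate is divided by patients who could not have had such an event. A result of no events is likewise credited with more patients than tested the module. The same applies to harm from balloon inflation, for patients whose balloon never inflated.

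At stake is how the safety result can be read. Someone who sees few or no device-related events over the arm, next to a statement about the entire system, could take the arm-level interval as the evidence for each module. The tables would not show how many patients stood behind each module or which module an event was attributed to. UrineFlow users are also chosen by the PI, so they may differ from the rest of the arm.

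**Working it through.** The documents give no safety rate, margin or precision target, so there is no safety figure to reproduce. The check asks what the arm-level figures imply for a partly used component.

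**Inputs**
- Group A size: 100 in the full study (9.1), 50 at this site (synopsis).
- Denominator: group A. This is inferred from reporting by study group and by arm (9.2.1, 9.2.5), because no safety set is defined. Section 7.1 treats randomised patients who do not receive the intervention as screen failures. Group A is therefore roughly those who received the system, though not necessarily every module.
- Number exposed, *n*: not stated. The values 75, 50, 25 and 10 below are assumptions.
- Interval: two-sided exact 95%, since the plan promises 95% intervals and two-tailed tests.

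**Step 1: who is exposed to what**
- UrineFlow: at PI discretion (5.2.2, 5.5).
- Balloon: present on every study tube; inflation only after detected reflux (1.3 c, 1.7).
- Feeding tube and pump: planned for all of group A.
- REE sensor: baseline measurement planned for all of group A (5.2.5, 5.5).

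A shortfall in exposure is built in for UrineFlow and possible for balloon inflation. It is not planned for the tube, pump or baseline REE.

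**Step 2: dilution of a rate**

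Arm-level rate = *f* × risk among users, where *f* is the fraction exposed. A 10% risk among users (illustrative) appears as 0.50 × 10% = 5.0% if half are exposed, and as 0.25 × 10% = 2.5% if a quarter are.

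**Step 3: upper limit with no events**

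Upper limit = 1 − 0.025^(1/*n*).

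| Patients exposed | Two-sided 95% upper limit |
|---|---|
| 100 (whole arm, full study) | 3.6% |
| 75 | 4.8% |
| 50 (also the whole arm at this site) | 7.1% |
| 25 | 13.7% |
| 10 | 30.8% |

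With 25 of 100 exposed, the component limit is 13.7/3.6, or about 3.8 times the arm-level limit. At this site the arm-level limit is 7.1%, against 13.7% with 25 exposed.

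**Step 4: how easily a real risk is missed**

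If the true risk among users were 5% (illustrative), the chance of seeing no events is 0.95^*n*: 0.6% with 100 exposed, 7.7% with 50 and 27.7% with 25.

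**The case against.** **The endpoint asks about the system as used.** It counts events related to any component, with modules connected where applicable. For that question all treated group A patients are a proper denominator, and the protocol sets no component-level margin or zero-event criterion. This stands. A reader might infer that the arm-level rate is wrong; the documents do not support that. The gap is that nothing else is reported, so the arm-level figure is the only one available for each module.

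**The problem is narrower than modularity suggests.** This also stands. A reader might infer that the REE sensor is diluted in the same way because it works only during ventilation. But the population is ventilated patients expected to remain so for at least 48 hours, and a baseline REE measurement is planned for all of group A. Nor can balloon exposure be called rare. Section 1.2.3 cites a study in which 88% of ventilated, tube-fed patients had at least one aspiration of gastric content in three days. That is not the device's reflux-detection rate. As a rough guide, though, 88 exposed of 100 gives 1 − 0.025^(1/88) = 4.1%, close to 3.6%. UrineFlow is the main case.

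**The size depends on numbers the plan does not give.** This is true. At 75 users the limit is 4.8% against 3.6%, a modest gap. The direction holds for any exposure below the full arm.

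**Attribution is not wholly lost.** Events are listed individually with a description, so the source of a few events could often be guessed. That is weaker than the examining clinician's judgement recorded at the time, and it supplies no exposed denominator.

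**Components act together.** Section 1.8.2 says that they must work as one system, so some events will not be attributable to a single module. The recording item therefore needs to allow more than one component, or undetermined.

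**Conclusion.** The point holds in a limited form. The plan states a safety endpoint for the entire system and any component, but reports only over the arm and without component attribution, although UrineFlow is optional and balloon inflation is conditional. For a component used in part of group A, the arm-level figures understate risk and uncertainty. With no events the two-sided 95% upper limit is 3.6% over 100 patients, against 7.1% with 50 exposed and 13.7% with 25.

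This rests on two assumptions: that the denominator is all of group A, which is the only one the plan offers, and that the exposure counts, which the documents do not give, are of this order. If nearly all of group A used UrineFlow, the effect would be small.

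A reader might also conclude that the entire-system statement should be confined to patients in whom every module was used. That does not follow. Such a subset would be selected by PI choice and by reflux after randomisation, and might not represent the system as intended to be used.

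**What to change.** Keep the arm-level tables and add the following to section 9.2.5:

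1. The number of patients connected to UrineFlow and their connected days, and the number of patients with at least one balloon inflation. Section 5.2.8 has the console record urine, reflux and all other system data, so these should be derivable from the logs. The sponsor should confirm that inflations are logged.
2. For each device-related AE or SAE, the implicated component or components, recorded on the AE page by the assessing clinician, with an option for undetermined.
3. Component-related events over exposed patients, with exact two-sided 95% confidence intervals.
4. The number exposed to each module, stated alongside any safety statement about the entire system.

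The cost is one item on the AE page and one table. Component-level intervals will be wider than the arm-level one, because fewer patients were exposed.

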1.1. Background

Patients hospitalized in the ICU often lack the inner ability to monitor and check basic functions. It therefore falls onto the shoulders of the medical staff and accompanying devices to take their place and care for the patients.

1.1.1. Reflux detection

Two common techniques for detecting refluxes are Esophageal Impedance Monitoring (EIM) and PH monitoring. Both involve inserting a small tube through the patient's nose into their esophagus and monitored over a period of time. These means are popular in the diagnosis of Gastroesophageal reflux disease (GERD).

1.1.2. Aspiration pneumonia prevention (in the ICU)

Common practice for preventing refluxes and aspiration in tube fed patients in the ICU include: placing the patient in a semi-Fowler's position; feeding at a low and constant rate (~50cc/hr) throughout the day; following the site Gastric Residual Volume (GRV) protocol; flush the catheter after administration of drugs to prevent occlusion; and, administration of Proton Pump Inhibitors (PPIs)¹.

1.1.3. GRV practices

Each site has their own protocol with regard to GRV practice, GRV protocol can vary with regards to the frequency, duration, volume, extraction technique and even what is done with the GRV once extracted.

For example, one site may perform GRV with a 100cc syringe every 4 hours. Promptly returning the suctioned GRV to the patient at the end of the procedure. While another site may connect a bag to the patient's feeding tube and hang it below the height of the patient's bed to slowly empty out the entire content of the patient's stomach over a two hours period, and discard it.

1.1.4. Optimal nutrition

Nutrition for ICU patients is prescribed by a dietitian upon admission based on a manual calculation using the Harris-Benedict equations. Occasionally a calorimeter or REE is implemented, but this is for extreme cases and not continuously monitored.

Regardless of the means used to prescribe the nutrition, GRV and reflux volume are not taken into consideration.

1.1.5. Urine meter

¹ Nutritional Support in ICU Patient. *Pierre Singer. ESPEN.*

Subject: smART Plus Comparative Study Protocol - Beilinson

The most common practice in the field for monitoring urine flow in the ICU is by manually examining the urine collection bag. This is done at best once an hour by a nurse and recorded in the patient's hospital records.

For exceptionally prone patient's there is a growing trend for automatic urine output monitoring. These devices utilize a range of weight-related technologies and provide real time monitoring of urine output and flow rates.

1.2. The Problems/Study Rationale

1.2.1. Malnutrition in the ICU

Many critically ill patients develop malnutrition during hospitalization. Malnutrition is a complication which adversely affects clinical outcomes, including length of hospital stay, morbidity, and mortality. The characteristics of ICU patients have changed during the last decade; they now tend to be older and their medical disorders more complex with frequent comorbidities. These factors may contribute to malnutrition in the ICU. Additionally, the combination of stress and undernutrition is associated with negative energy balances and the loss of lean body mass².

Mechanically ventilated patients are unable to take food orally and therefore are dependent on enteral nutrition for provision of both energy and protein requirements. Many critically ill patients often have pre-existing conditions, including malnutrition. All of this predisposes patients to nutrition deficits, muscle wasting, delayed wound healing, slower recovery, and increased risk of morbidity and mortality. There is a consensus that supplemental nutrition support is needed and improves outcomes for patients³.

Providing adequate energy via nutrition support to the mechanically ventilated patient is critical. In the mechanically ventilated patient, overfeeding, even for short periods of time, can lead to hyperglycemia and increases time on the ventilator. Conversely, an increasing caloric deficit (persistent underfeeding) also increases time on the ventilator. Providing early nutritional intervention may shorten hospital stays by 2 days, lower readmission rates by 27% and save \$3,800 per patient.

Indirect calorimetry is the recommended method for determining patients' resting energy expenditure (REE). A 2015 estimate showed that only 2% of ICUs were regularly using indirect calorimetry. Predictive equations have therefore been the most commonly practiced method of determining energy needs; however, the literature clearly indicates that each equation has a large potential for error. This makes it difficult to accurately predict an individual patient's energy requirements during critical illness. In general, predictive equations estimate accurately only 50% of the time in ICU patients⁴.

² Thibault R, Pichard C. Nutrition and clinical outcome in intensive care patients. Curr Opin Clin Nutr Metab Care 2010; 13(2):177-83

³ Allen, K., Hoffman, L. Enteral Nutrition in the Mechanically Ventilated Patient. Nutr in Clin Pract. Vol 00 2009/1-18. DOI: 10.1002/ncp.10242.

⁴ Allen, K., Hoffman, L. Enteral Nutrition in the Mechanically Ventilated Patient. Nutr in Clin Pract. Vol 00 2009/1-18. DOI: 10.1002/ncp.10242.

Subject: smART Plus Comparative Study Protocol - Beilinson

The American Association for Parenteral and Enteral Nutrition recommends that for patients who are at high risk for malnutrition, efforts should be made to provide >80% of the estimated or calculated energy and protein goal within 48–72 hours, starting with half the patient's calorie goal with the rate slowly increasing over time, in order to achieve the clinical benefit of enteral nutrition over the first week of hospitalization⁵. However, studies have shown that more than 74% of ICU patients failed to receive at least 80% of their proscribed nutrition⁶. Gastric retention and intolerance are usually measured by means of extraction and assessment of the gastric residual volume (GRV). However, the nutrients lost through GRV assessments are often not compensated for. In addition, feeding is regularly paused for medical intervention and imaging occurring outside of the unit.

